#### **5.6.1.5. COVID-19 case**

At each visit the participant will be asked if they have had a private/off-study COVID-19 test. If a participant receives a positive SARS-CoV-2 result from a private/off-study test during the study, and the positive result occurs within 28 days after vaccination, the event will be reported as an AE. If it occurs after 28 days, the event will be recorded as an SAE only if the event qualifies as serious. If the event occurs after 28 days, and it is not serious, it will not be reported in the eCRF.

Any positive SARS-CoV-2 result should be recorded in the eCRF.

A listing with all COVID cases throughout the study will be created including the severity, the onset, the duration and any other relevant information for the event will be created.

## **5.6.2. Other Safety Analyses**

### **5.6.2.1. Clinical Laboratory Tests**

Local laboratory data (normal, abnormal or graded, when available) will be listed and/or tabulated by participant and time point.

Local lab results reported without units/ranges are not evaluable for grading and severity. Such events will be displayed in a separate listing.

### **5.6.2.2. Vital Signs and Physical Examination Findings**

Baseline and emerging vital signs abnormalities after vaccination will be listed based on the abnormality gradings in Appendix 7 (Section 6.7). An abnormality will be considered as emerging in a particular period if it is worse than the baseline value. If the baseline is missing, the abnormality is always considered emerging.

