Approx. blood draw per day, mL:		30		30		15		15	● ³ 15
Approx. cumulative blood draw, mL:		30		60		75		90	

●¹ pre vaccination; ●² pre and post vaccination; ●³ blood samples for immunogenicity will only be taken if the early exit visit is at least 10 days after the previous immunogenicity blood draw; ●⁴ if within 7 days of the vaccination; ●⁵ if within 28 days of the vaccination.

The phone call or these visits (including their window) are to be scheduled relative to the actual day of the previous vaccination, indicated as Visit Timing days/weeks post vaccination.

- Screening can be performed within 28 days prior to the first study vaccination or on the day of vaccination. If screening is performed on the day of vaccination, Visit 1 and Visit 2 will coincide on Day 1. Screening must be completed, and all eligibility criteria must be fulfilled prior to randomization and vaccination.
- If a participant shows COVID 19 like symptoms, the participant should contact the site for guidance and must follow their local country and site level recommendations for COVID 19.
- The site will contact the participant 7 days post vaccination 1, and 7 days post vaccination 2 to enquire about compliance and severe symptoms reported on the participant diary.

- d. For those participants who are unable to continue participation in the study, but for whom consent is not withdrawn, an early exit visit could be conducted. Participants who wish to withdraw consent from participation in the study could be followed up for safety purposes if desired. This includes safety assessments of the early exit visit (no blood sampling for immunogenicity) and documenting the reason.
- e. Signing of the ICF should be done before any study related activities.
- f. History of SARS CoV 2 vaccination (name/manufacturer of the vaccine and date of administration) \geq 6 months prior to the study will be collected in the SARS CoV 2 Vaccination page in the eCRF.
- g. A full physical examination, including height and body weight, will be carried out at screening. At other clinic visits, a symptom directed physical examination can be performed in case of participant's complaints.

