9.4.2. Inferential Endpoints

The NI immunogenicity objectives will be assessed by calculating:

- the 2-sided 95% CIs for the difference in log-transformed HI antibody titers against each of the 4 influenza vaccine strains at 28 days after the administration of the seasonal influenza vaccine between the Control and the CoAd group for the *standard-dose*.
- the 2-sided 95% CIs for the difference in log-transformed S-ELISA titers at 28 days after the administration of Ad26.COV2.S vaccine between the Control and the CoAd group for the *standard-dose*.

For HI antibody titers against each of the 4 influenza vaccine strains and for S-ELISA titers, an analysis of variance (ANOVA) model will be fitted with the respective titers as dependent variable and group (Control or CoAd), age category (as stratified), previous SARS-CoV-2 vaccination (as stratified), and baseline S-ELISA titers as independent variable. Based on these ANOVA models, the CIs around the difference will be calculated and will be back transformed (by exponentiation) to CIs around a GMC or GMT ratio (Control group/CoAd group), respectively, and compared to the NI margin of 1.5.

Only if the upper bound of the 2-sided 95% CI for the GMT or GMC ratio (Control group/CoAd group), respectively, of the HI antibody titer for each of the 4 vaccine strains and for S-ELISA lies below 1.5, NI of co-administration versus separate administration will be concluded for both vaccines (seasonal influenza vaccine and Ad26.COV2.S vaccine). If 1 or more confidence limits for the GMT or GMC ratio exceed 1.5, non-inferiority cannot be concluded.

For immunogenicity, baseline is considered as the last assessment pre-vaccination (ie, it corresponds to Day 1 for CoAd groups or influenza vaccine alone, or to Day 29 for Ad26.COV2.S vaccine). In a sensitivity analysis, different variances between the groups will be allowed. Therefore, the CIs will be calculated via Welch's ANOVA.

The assessment of the primary endpoints will be performed on individuals who have been previously vaccinated with different types of COVID-19 vaccines. This factor brings a level of variability of immune responses that is unknown.

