9.4.5. Safety Analyses

No formal statistical testing of safety data is planned. All safety data will be analyzed descriptively by group. All safety analyses will be based on the FAS.

Adverse Events

The verbatim terms used in the eCRF by investigators to identify AEs will be coded using the Medical Dictionary for Regulatory Activities (MedDRA). All reported AEs with onset during the active vaccination phase (ie, AEs occurring after vaccination up to 28 days post-vaccination), and all SAEs/MAAEs/AESIs will be included in the analysis. (S)AEs caused by molecularly confirmed SARS-CoV-2 infection will be removed at the analysis level from the (S)AE listings and tables and presented separately. For each AE, the percentage of participants who experience at least 1 occurrence of the given event will be summarized by vaccine group.

Summaries, listings, datasets, or participant narratives may be provided, as appropriate, for those participants who die, who discontinue study vaccine due to an AE, or who experience a severe AE, an AESI, or an SAE.

Solicited local (at injection site) and systemic AEs will be summarized descriptively. The number and percentages of participants with at least one solicited local (at injection site) or systemic AE will be presented. The frequencies by vaccine group as well as frequencies according to severity and duration will be described for solicited AEs. Frequencies of unsolicited AEs, separately for all and vaccination-related only, will be presented by System Organ Class and preferred term, while those of solicited AEs will be presented only by preferred term.

Clinical Laboratory Tests

Laboratory data (abnormal or graded, when available) will be listed and/or tabulated by participant and time point.

Vital Signs

Vital signs including temperature, pulse/heart rate, respiratory rate, and blood pressure (systolic and diastolic) will be summarized over time, using descriptive statistics and/or graphically. The percentage of participants with values beyond clinically important limits will be summarized.

Physical Examinations

Physical examination findings will be summarized at baseline. Physical examination abnormal findings will be listed.

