### **5.6.1.2. Analysis of Adverse Events**

Safety analyses will be performed on the FAS. Continuous variables will be summarized using the following statistics, as appropriate: number of observations, median, minimum, and maximum. Frequencies and percentages (one decimal place) will be generated for categorical variables. No formal comparisons between groups will be provided.

Safety data will be analyzed and presented by study intervention and phase. Denominator for the percentages is the number of participants in the considered population and phase for a certain regimen (incidence per 100 participants/phase).

Number and percentage of participants with at least one particular AE (unsolicited/solicited) will be tabulated. Unsolicited AEs will be summarized by System Organ Class and Preferred Term. Solicited AEs will be summarized by class (administration site, systemic) and preferred term.

For solicited AEs, the following tables will be provided: summary, by worst severity grade, at least grade 3, related (systemic only), time to onset (in days) and duration (in days). Note: Duration is defined as number of days from the start of the event until resolution of the event. The time to first onset is defined as (date of first onset – reference date + 1). The reference date is the start date of the vaccination period.

A tabulation of the distribution of temperatures per half degree intervals will also be provided.

For unsolicited AEs, the following tables will be provided: summary table (including SAE, fatal outcome, discontinuation and AESI), all events, most frequent, at least grade 3, permanent stop of vaccine, related, SAE, related SAE, potential AESI and AESI.

Unsolicited non-serious adverse events collected outside the 28-day period following the vaccination will be presented through listings.

Listings and/or participant narratives will be provided as appropriate, for those participants with a fatal outcome, discontinue study vaccinations due to an AE, discontinue study due to an AE, or experienced a severe SAE, or an AESI event.

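### SAP 5.6.2.2 replaces the protocol's by-group vital-sign summaries with a listing, does not record the change, and leaves the baseline for emerging abnormalities undefined

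*SAP*

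**What the plan says.** Protocol 9.4.5 states the general rule "All safety data will be analyzed descriptively by group". For vital signs it says that temperature, pulse/heart rate, respiratory rate and blood pressure "will be summarized over time, using descriptive statistics and/or graphically", and adds: "The percentage of participants with values beyond clinically important limits will be summarized". Physical-examination findings are to be summarised at baseline.

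SAP 5.6.2.2 covers the same ground in three sentences. The first is "Baseline and emerging vital signs abnormalities after vaccination will be listed based on the abnormality gradings in Appendix 7 (Section 6.7"). The second is "An abnormality will be considered as emerging in a particular period if it is worse than the baseline value". The third treats any abnormality as emerging when the baseline is missing. The section heading names physical examination, but the text does not mention it.

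The protocol's Schedule of Activities (1.3.1) marks vital signs on Day 1 and Day 29 as "pre and post vaccination". They are taken again on Day 57 and at Week 28. CoAd receives Ad26.COV2.S on Day 1 and Control receives it on Day 29.

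**The concern.** There are two gaps. First, the SAP is meant to carry out protocol 9.4, yet its vital-signs section reduces a summary with percentages to a listing of abnormal values. A listing does not show whether graded blood-pressure or pulse changes were more frequent when the vaccines were given together than when they were given apart. Safety of Ad26.COV2.S given separately or with influenza vaccine is a secondary objective, so the by-group description is the useful output.

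Second, the emerging flag depends on a reference that is not defined. The SAP has two post-dose periods, and the two arms receive Ad26.COV2.S in different ones. If the reference is fixed at Day 1, CoAd's first reading after Ad26.COV2.S is compared with one from the same visit, while Control's is compared with one from four weeks before. Ordinary visit-to-visit variation would then produce somewhat more flags in Control.

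**Working it through.** **Outputs, side by side**

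| Item | Protocol 9.4.5 | SAP 5.6.2.2 |
|---|---|---|
| Vital signs over time | Descriptive statistics and/or graphs | Not specified |
| Percentage beyond limits | Planned | Not specified |
| Presentation by group | Stated for all safety data | Not stated |
| Physical examination at baseline | Summary | Not mentioned |
| Listing of abnormal vital signs | Not specified | Specified |

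SAP Appendix 2, which records changes to protocol-planned analyses, covers the ANOVA strata and the HI analysis of non-matched strains. It does not mention vital signs or physical examination.

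**Which baseline?** The SAP defines a baseline only in 5.3.2, and only for immunogenicity. Protocol 9.4.2 has the same restriction: "For immunogenicity, baseline is considered as the last assessment pre-vaccination". Two readings are possible for vital signs at Control's Day 29 dose:

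- Day 1 pre-dose: the reference is 28 days old on schedule. With the Day 29 window of -3/+7 days, the range is 28 - 3 = 25 to 28 + 7 = 35 days.
- Last reading before that vaccination: the reference is Day 29 pre-dose, so the gap is 0 days.

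**Value or grade?** Worse than the baseline value can mean a worse number or a worse grade. In SAP Appendix 7, systolic 141 to 150 mmHg is Grade 1. A change from 142 to 143 is flagged under a value rule but not under a grade rule.

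**Size of any artefact.** The documents give no variability for vital signs, so these inputs are assumptions. Systolic pressure = person + visit effect + within-visit error, with mean 130, between-person SD 13, visit SD 8, within-visit SD 5, no vaccine effect, and the Appendix 7 cut-offs. A Day 1 baseline is assumed except where stated. The comparison is CoAd after its Day 1 dose against Control after its Day 29 dose.

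*Single reading just after Ad26.COV2.S:*

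| Rule | CoAd | Control | Ratio |
|---|---|---|---|
| Value | 14.9% | 17.9% | 17.9/14.9 = 1.20 |
| Grade | 9.4% | 14.7% | 14.7/9.4 = 1.56 |

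The SAP, however, flags per period, and SAP 5.1.2 runs each post-dose period to 28 days after vaccination. On schedule, CoAd's post-dose 1 therefore contains the Day 1 post-dose and Day 29 pre-dose readings. Control's post-dose 2 contains the Day 29 post-dose and Day 57 readings.

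*Any flag in the period:*

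| Rule | CoAd post-dose 1 | Control post-dose 2 | Ratio | Range of ratio |
|---|---|---|---|---|
| Value | 27.4% | 28.2% | 28.2/27.4 = 1.03 | 1.01 to 1.07 |
| Grade | 20.8% | 23.6% | 23.6/20.8 = 1.13 | 1.09 to 1.23 |

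The ranges cover mean 126 to 135, visit SD 6 to 10 and within-visit SD 4 to 5. If each period instead uses its own last pre-dose reading, Control's base-case percentages become 27.4% and 20.8%, equal to CoAd's, so the ratio is 1.0 under both rules.

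**The case against.** The strongest reply is that the SAP should be read as a whole. SAP 5.6.1.2 says "Safety data will be analyzed and presented by study intervention and phase", calls for frequencies and percentages of categorical variables, and promises a tabulation of temperatures by half degree. The SAP introduction says that a separate Data Presentation Specification will detail the outputs. Vital signs are not among the listed safety endpoints, and neither document plans formal testing of safety data.

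Part of this stands. A reader might infer that vital signs are never compared between groups. The documents do not support that: temperature is tabulated, and the output specification, which is not available here, may add more. What is lost is descriptive presentation, not a planned test. But the general text sits under the analysis of adverse events and names no output for pulse, blood pressure or respiratory rate. The SAP also presents itself as containing what is needed for the complete safety analysis.

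A reader might also infer that every period is judged against one Day 1 baseline, and that the plan is therefore biased in favour of co-administration. The text does not establish this. The reference is undefined, and the words about a particular period fit a period-specific baseline too. A listing yields no estimate to be biased. Presentation by phase compares the arms within the same period, where both share the same reference under either reading. The artefact needs a Day 1 baseline together with a comparison of CoAd post-dose 1 against Control post-dose 2. Likewise, the reading that a rise of 1 mmHg is always flagged is only one of two, because abnormalities are defined by grade in the preceding sentence.

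**Conclusion.** The point holds for the outputs, and it rests on text alone. SAP 5.6.2.2 drops the protocol's summary over time, the percentage beyond clinically important limits and the baseline physical-examination summary, and Appendix 2 does not record this. As written, no by-group descriptive output is specified for pulse, blood pressure or respiratory rate.

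On baseline, the established defect is a missing definition, with a possible gap of 0 or about 28 days for Control's Ad26.COV2.S dose. A claim of material bias is not supported. Even with a Day 1 baseline and the cross-period comparison, the spurious ratio is about 1.0 to 1.1 (value rule) or 1.1 to 1.2 (grade rule), given the assumed variability and on-schedule visits. There is no excess if the last pre-dose reading is used. The change should be made because it restores a protocol commitment and removes an ambiguity at little cost, not because a primary conclusion is at risk.

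**What to change.** Revise SAP 5.6.2.2 as follows:

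- Give descriptive statistics for each vital sign by group and time point.
- For each post-dose period, give n (%) of participants with graded abnormalities and with emerging abnormalities, by group.
- Define emerging as a toxicity grade higher than at the last reading before that vaccination: Day 1 pre-dose for post-dose 1, Day 29 pre-dose for post-dose 2.
- Restore the baseline physical-examination summary.
- Keep the listing as a supplement.

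If the sponsor prefers a listing only, Appendix 2 should record that as a change from protocol 9.4.5, and the baseline definition is still needed. The cost is SAP wording and a few tables. The schedule already collects every reading required.

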## **5.7. Other Analyses**

### **5.7.1. Subgroup Analysis**

For exploratory purpose, subgroup analyses for the primary endpoints (and vaccine-naïve participants) related to humoral response will be done (but are not limited) for the following subgroups if significant balance is achieved:

#### **5.7.1.1. Age**

This exploratory analysis intents to assess the effect of Age, regarding the humoral response.

Subgroup	Definition
Age Group	
 
• <math>\geq 18</math> to <math>\leq 64</math> years
 
• <math>\geq 65</math> years
 

#### **5.7.1.2. Humoral responses to Ad26.COV2.S based on the SARS-CoV-2 serostatus at baseline (N-serology) and the previous history of COVID-19 vaccination at entry**

This exploratory analysis intents to assess the effect of previous infection or not by natural SARS-CoV-2.

Subgroup	Definition
Previously natural SARS-CoV-2 infected participants	
 
• Previously infected
 
• Not previously infected
 

No specific actions are made to balance previously infected participants. The analysis will be conducted as exploratory purpose.

Subgroup	Definition
Participants receiving primary series vaccine at entry	
 
• Vaxzevria [AstraZeneca]
 
• Comirnaty [Pfizer-BioNTech]
 
• SpikeVax [Moderna]
 
• Ad26.COV2-S [Janssen]
 
 
Or
 
 
• mRNA
 
• Adeno based
 

The combination of these 2 factors will be assessed if the groups numbers are deemed relevant.

#### **5.7.1.3. Humoral responses to influenza vaccine based on the SARS-CoV-2 serostatus at baseline (N-serology) and the previous history of COVID-19 vaccination at entry**

This exploratory analysis intents to assess the effect of primary series vaccine at study entry (Vaxzevria [AstraZeneca], Comirnaty [Pfizer-BioNTech], SpikeVax [Moderna], and Ad26.COV2-S [Janssen]) and serostatus at baseline. The combination of these 2 factors will be assessed if the groups numbers are deemed relevant.

HI analysis will be conducted as an exploratory endpoint to evaluate immune response elicited by the co-administered influenza based on COVID-19 vaccine serostatus and pre-vaccination history.

The serological response to vaccination will be measured by HI titers against each of the 4 influenza vaccine strains at 28 days after the administration of a seasonal quadrivalent (high-dose and standard-dose) influenza vaccine. Then, the geometric mean titer of HI antibodies at 28 days after the administration of a seasonal quadrivalent (high-dose and standard-dose) influenza vaccine will be described for each subgroup.

#### **5.7.2. Primary and Final Analysis**

The primary analysis of safety and immunogenicity will be performed when all participants have completed the 28 days after the second study vaccination visit or discontinued earlier. The primary

analysis will be performed based on sponsor's unblinded data (sponsor, study-site personnel and participants will remain blinded during the treatment phase up to the database lock).

A final analysis will be performed when all participants have completed the 6 months follow-up period after the second vaccination or discontinued earlier.

### **5.8. Data Monitoring Committee (DMC)**

No Data Monitoring Committee (DMC) has been planned for this study.

### **5.9. Interim Analyses**

No interim analyses will be performed.

## 6. SUPPORTING DOCUMENTATION

### 6.1. Appendix 1 List of Abbreviations

Ad26	adenovirus serotype 26
ADaM	Analysis Data Model
AE	adverse event
AESI	adverse events of special interest
ANOVA	analysis of variance
BMI	body mass index
CI	confidence interval
COVID-19	COVID-19 coronavirus disease-2019
CRF	case report form
CSR	Clinical Study Report
CTP	clinical trial protocol
CV	coefficient of variation
DPS	Data Presentation Specifications
eCRF	electronic case report form
ELISA	enzyme-linked immunosorbent assay
FAS	full analysis set
FDA	Food and Drug Administration
GMT	geometric mean titre
HAI	hemagglutination inhibition assay
HI	hemagglutination inhibition
ICH	International Conference on Harmonisation
IWRS	interactive web response system
LLOQ	lower limit of quantification
MedDRA	Medical Dictionary for Regulatory Activities
MAAE	medically attended adverse events
PI	principal investigator
PP	per protocol
SAE	serious adverse event
SAP	Statistical Analysis Plan
SD	standard deviation
SDTM	Study Data Tabulation Model
SE	standard error
SMQs	standardised MedDRA queries
TEAE	treatment-emergent adverse event
ULOQ	upper limit of quantification
WHO	World Health Organization
WHO-DD	World Health Organization Drug Dictionary

## **6.2. Appendix 2 Changes to Protocol-Planned Analyses**

For HI antibody titers against each of the 4 influenza vaccine strains and for S-ELISA titers, an analysis of variance (ANOVA) model will be fitted with the respective titers as dependent variable and group (Control or CoAd), age category (as stratified), previous SARS-CoV-2 vaccination (as collected), and baseline S-ELISA titers as independent variable.

The strata will be based on the values in the database for vaccination history (which may differ to the strata as recorded in IWRS).

In order to evaluate the cross-reactivity between HAs, we will analyze the HI responses to mis/unmatched vaccine strains. This analysis will be performed in a subset of participants, namely, study participants that are 65 yo and older. Samples will be tested specifically for the H3N2 and the B/Victoria influenza strains. Participants corresponding to Groups 1 and 2 will be analyzed for the following non-matched strains: A/Tasmania and B/Washington. Participants corresponding to Groups 3 and 4 will be analyzed for the following non-matched strains: A/Cambodia and B/Victoria.

